#### **8.4 Definition of a Dose Limiting Toxicity (DLT)**

Subjects will continue on IP twice daily from day 1 of RT to the evening prior to their 1-month post-RT follow-up appointment with their Radiation Oncologist or unless instructed to stop IP as described elsewhere. If the subject meets the criteria listed above to be taken off the study, they will discontinue IP, but all assessments will continue to be collected. There are no known pre-specified DLTs associated with the IP.

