#### **9.6 Early Treatment Termination**

Subjects that terminate IP treatment prior to completing the planned treatment portion of the protocol will still be seen as per the study schedule and have an early termination visit at their 1-month post-RT follow-up appointment with their Radiation Oncologist. However, if the subject decides to withdraw from the study, no further information will be collected.

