### **15. REMOVAL OF SUBJECTS**

Subjects have the right to withdraw from the study at any time and for any reason without prejudice to their future medical care by the physician or at the institution. If this occurs, the investigator, or designee, is to discuss with the subject the safe and appropriate processes for discontinuation from the investigational product, intervention or device.

Subjects that wish to discontinue active IP treatment/intervention/device may elect to continue with the other protocol required assessments. The investigator should discuss with the subject the options for continuation of the study schedule of assessments (i.e. blood work, scans, physical exams, diaries) and collection of data, including endpoints and adverse events.

The investigator or designee must document the change in status of the subject's participation in the study and as applicable, the level of follow up that is agreed to

by the subject (i.e. agrees to follow up exams, adverse event review, phone contact, but not to further treatment and/or procedures).

Subject withdrawal of consent for a study indicates that the subject does not wish to receive further protocol required therapies or procedures, and the subject does not wish to, or is unable to continue further study participation. Subject data only up to the time when consent is withdrawn will be included in the analysis of the study.

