## **16. STATISTICAL CONSIDERATIONS**

The primary statistical analysis will compare the proportion of patients who develop severe OM ( $\geq$ WHO Grade 3) in patients randomized to ClōSYS Oral Rinse versus placebo. Analysis will be performed by estimating the proportion with exact 95% binomial confidence interval for each group separately. Statistical testing will use a chi-square test. As an alternative, Fisher's Exact Test will be used if the minimum expected value is  $< 5$ .

The secondary statistical endpoint of time to onset of severe OM will be tabulated and the median week to onset will be computed for each group. Comparison will be performed using a Wilcoxon Rank Sum Test (as the values are unlikely to be normally distributed). Duration of severe OM (number of weeks) will be analyzed similarly. The proportion of patients in each group with RT interruption will be tabulated and compared using a chi-square test.

The longitudinal measurements of the OMWQ and PRO-CTCAE, microbiome components and pro-inflammatory cytokines will be compared between groups using a linear mixed-effects model to account for the correlation among the measurements within an individual.

To justify the proposed sample size, we assume that 9/10 (90%) of the placebo control patients will experience severe OM within the 6-week period. Ten patients per group will allow us to detect a decrease to 40% (4/10) in the patients randomized to ClōSYS® Unflavored Oral Rinse with 81% statistical power (assuming a one-sided alpha of 0.05).

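### Time to onset and duration of severe OM are compared by medians and a Wilcoxon test with no rule for patients who have no onset week or who withdraw; Kaplan-Meier with a log-rank test suits onset better, and duration needs defined values

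*Combined protocol and SAP*

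**What the plan says.** Section 16 (Statistical Considerations) states that "time to onset of severe OM will be tabulated and the median week to onset will be computed for each group". On the test it says: "Comparison will be performed using a Wilcoxon Rank Sum Test (as the values are unlikely to be normally distributed". Non-normality is the only reason given. On the next endpoint it says: "Duration of severe OM (number of weeks) will be analyzed similarly".

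The sample-size paragraph of the same section supplies the rates. For placebo, "we assume that 9/10 (90%) of the placebo control patients will experience severe OM within the 6-week period"; for the rinse, "Ten patients per group will allow us to detect a decrease to 40% (4/10".

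On patients who leave, Section 9.6 says that "if the subject decides to withdraw from the study, no further information will be collected", and Section 15 that "Subject data only up to the time when consent is withdrawn will be included in the analysis of the study". Patients who only stop the rinse are treated differently: under Section 8.4 "they will discontinue IP, but all assessments will continue to be collected".

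Section 7.1 and the Section 26 schedule have WHO grading at every weekly on-treatment visit and at the 1-month visit. Section 2.4 lists OM scoring at baseline, weeks 2, 4 and 6, and the 1-month visit only. No section mentions censoring, a survival method, or a value for a patient who never reaches Grade 3.

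**The concern.** A median week and a rank test need one number per patient. On the plan's own assumptions about 7 of 20 patients have no onset week, most of them on the rinse, and a withdrawn patient has only a lower limit for it. The text leaves at least three readings open: analyse only patients with an onset; rank event-free patients last; or leave withdrawn patients out, which the undefined word 'evaluable' in Section 1.4 might mean. They give very different results, and the choice would be made after the data are seen.

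Duration inherits the gap. No value is given for a patient who is never severe. An episode still open when RT ends is next graded at the 1-month visit, so its number of weeks is undefined. Section 4.2 names both time to onset and duration among the trial's hypotheses.

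**Working it through.** **Inputs.** From Section 16: 10 per group, 90% v 40%, one-sided alpha 0.05, 81% power. From Sections 1.4 and 2.3: 24 randomised 1:1, with 4 extra for drop-out or non-compliance. From Section 9.5: follow-up window +21 days. The weeks of onset and withdrawal are assumptions, varied below.

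**The plan's own figure.** The arcsine formula gives h = 2·asin(√0.9) − 2·asin(√0.4) = 1.129, and Φ(1.129·√5 − 1.645) = 81.0%. The stated 81% is reproduced, so the rates can be taken at face value.

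**Patients with no onset week.** Placebo 10 × (1 − 0.90) = 1; rinse 10 × (1 − 0.40) = 6. With Binomial(10, 0.4), the chance of 4 or fewer onsets on the rinse is 63%, so the rinse median is usually not reached. A median among cases only would show about week 3 v week 2 under a constant hazard, and about 3.8 weeks in both arms if the rinse prevents cases without shifting their timing.

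**Formula check for log-rank.** Under proportional hazards HR = ln(0.6)/ln(0.1) = 0.222, with 9 + 4 = 13 events. Then √(13/4) × |ln 0.222| − 1.645 = 1.07, or about 86% one-sided power.

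**Simulated power, 10 per arm, weekly grades for 6 weeks, complete follow-up, one-sided 0.05.** The constant hazard uses a weekly onset probability of 1 − (1 − p)^(1/6), which is 0.319 on placebo and 0.082 on the rinse.

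| Assumed onset | Cases only | Event-free ranked last | Stratified permutation log-rank |
|---|---|---|---|
| Constant hazard | 17% | 81% | 83% |
| None in weeks 1-2 | 16% | 80% | 82% |
| Weeks 3-6 in both arms | 4% | 65% | 73% |
| Rinse cases a week later | 32% | 88% | 87% |

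Separate runs of the first row gave 16%, 80-81% and 84-86%, the last with asymptotic log-rank tests. An unstratified permutation log-rank gave 85%. Two-sided, the first row is 9%, 69% and 73%.

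**Power with withdrawal.** With 12 per arm and 4 of 24 lost at random in weeks 1-3, power for log-rank / last rank with withdrawals counted as never affected / last rank with withdrawals left out is:
- constant hazard: 86 / 82 / 79%
- none in weeks 1-2: 84 / 75 / 80%
- weeks 3-6 in both arms: 73 / 61 / 64%
- rinse a week later: 89 / 85 / 88%

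**Null error with withdrawal (90% in both arms).** Averaged over random splits, every method has about 5%. Given the split, they differ.
- 3 rinse v 1 placebo, probability C(12,3)·12/C(24,4) = 2640/10626 = 25%: last rank 6-10%.
- 4 v 0, probability C(12,4)/C(24,4) = 495/10626 = 5%: last rank 8-33%. The low end is a constant hazard; the high end has later onset and very early withdrawal.
- Log-rank stays near 5% in both. If instead the earliest-onset patients leave the week before onset, its error is 12-14% at 3 v 1 and 23-25% at 4 v 0. Counting each withdrawal as an event then gives 4-5%.

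**Duration, weeks 1-6.** With complete follow-up, Wilcoxon power is 65-82% in all patients with 0 for never severe, and 3-17% in cases only. For withdrawn patients, one-sided null error is:
- using only the visits observed: 9-10% at 3 v 1 and 24-32% at 4 v 0, less if they were graded more often before leaving
- leaving them out: 4-5% in both
- counting missing visits as severe: below 1% at 3 v 1

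**Unseen gap after RT.** 30 to 51 days: 30/7 = 4.3 to 51/7 = 7.3 weeks.

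**The case against.** The best defence is that the Wilcoxon test can be used. A reader might infer that six event-free patients in ten defeat it. They do not: with complete follow-up, ranking them tied last is valid and costs a few points of power under a constant hazard (about 80% v 83-85%). It costs nothing if rinse cases start later, and log-rank shows no clear gain if grades exist only at weeks 2, 4 and 6. That defence stands. But the plan does not state the rule, and the rule mishandles early withdrawal.

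A reader might also infer that the plan commits to cases only. It does not; the text is silent, and the 16% belongs to one reading of it.

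Nor do the documents show that stratifying is needed. The stratified test gains only if the strata differ in risk, and the documents give no stratum risks.

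Finally, the withdrawal settings may be pessimistic. Sections 8.4 and 9.6 keep grading patients who only stop the rinse, so fewer than four may be lost. With two lost at random, power under a constant hazard is 88 / 84 / 83%, in the order used above. The 4 v 0 split is uncommon even if four are lost. This limits the size of the problem but does not supply the missing rule.

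**Conclusion.** The concern holds as a gap in two secondary analyses, and should be fixed before the data are seen. One sentence of the plan allows onset analyses with one-sided power from about 4% to over 80%, depending on the reading and on timing that must be assumed. Most of that range comes from the cases-only reading. Log-rank's advantage over a stated last-rank rule is modest and comes mainly when patients are lost early, and it rests on withdrawal being unrelated to mucositis. For duration, the choice for withdrawn patients matters as much: scoring them on observed visits alone favours the arm that loses more patients. The primary comparison of proportions is not touched by this point.

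**What to change.** **Onset.** In all randomised patients, report Kaplan-Meier curves by arm and a log-rank test with a permutation p-value. Stratifying by concurrent systemic therapy, the randomisation factor in Section 7.1, is reasonable but not essential. Use the weekly on-treatment grades, and reconcile Section 2.4 with Sections 7.1 and 26. Censor patients without severe OM at their last on-treatment assessment. Give the median as not reached where that applies. Report a first Grade 3 seen at the 1-month visit separately, because its week is unknown. State the assumption about withdrawal, and add one sensitivity analysis that counts a withdrawal before onset as an event at the next visit.

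**Duration.** Keep the Wilcoxon test, with 0 for patients who are never severe. Count on-treatment visits graded 3 or higher in weeks 1-6, and report week 7 and the 1-month grade separately. Section 6.2 admits 5-week courses, so say how week 6 counts for them. Make the main analysis the one in patients with complete on-treatment grading. Show observed-visits and missing-as-severe analyses as sensitivity only.

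**Cost.** A short addition to Section 16 and a little more analysis work. No new data are needed, since weekly grades are already scheduled. Leaving withdrawn patients out loses some power for duration.

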## 1.4 Patient Population

Eligible subjects must be able to understand and sign the study specific subject consent form. They must be  $\geq$ 18 years of age, have a Karnofsky Performance Status Scale (KPS) of  $\geq$ 60 with confirmed histologic or cytologic diagnosis of HNC (stage I-IV) for which they are receiving definitive or post-operative treatment with either RT alone or in combination with systemic therapy. Subjects may not have previous allergies to chlorine dioxide products and must fulfill the inclusion and exclusion criteria found in Section 6. Approximately 24 subjects will be randomized in a 1:1 ratio to stabilized chlorine dioxide rinse and placebo rinse. Twenty evaluable subjects (10 in each group) are needed in this pilot study to meet 81% statistical power (assuming a one-sided alpha of 0.05). We plan to recruit an additional 4 subjects to account for a 20% drop out/study non-compliance rate to ensure we have 20 evaluable subjects.

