## 2. STUDY DESIGN

### 2.1 Phase

This is a Phase II, single center, prospective, randomized, double-blind, placebo-controlled study. Approximately 24 subjects will be randomized in a 1:1 ratio to stabilized chlorine dioxide oral rinse and placebo oral rinse.

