## 2.3 Number of subjects

[figure not shown]
Approximately 24 will be recruited for this pilot study. Twenty evaluable subjects are needed to meet 81% statistical power (assuming a one-sided alpha of 0.05). We plan to recruit 4 additional subjects to account for a 20% drop out/study non-compliance rate.

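### The 81% power does not describe the planned primary test: the chi-square/Fisher rule has about 67% power one-sided (47% if run two-sided)

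*Combined protocol and SAP*

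**What the plan says.** Section 16 gives both the primary test and the sample size argument.

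- **Test.** The proportions with severe OM (WHO grade 3 or higher) are compared by chi-square. As the alternative, Fisher's "Exact Test will be used if the minimum expected value is" below 5. This text does not say whether the test is one- or two-sided.
- **Planning rates.** For placebo, "we assume that 9/10 (90%) of the placebo control patients will experience severe OM within the 6-week period". For the active rinse, "Ten patients per group will allow us to detect a decrease to 40% (4/10) in the patients randomized to" it, "with 81% statistical power (assuming a one-sided alpha of 0.05").
- **Repeats.** Section 1.4: "Twenty evaluable subjects (10 in each group) are needed in this pilot study to meet 81% statistical power". Section 2.3: "Twenty evaluable subjects are needed to meet 81% statistical power (assuming a one-sided alpha of 0.05").

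No section names the test or formula behind the 81%.

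**The concern.** A power figure should belong to the test that will be run. At 10 per group Fisher's exact test is clearly more conservative than the uncorrected chi-square test, and with a planned event rate of 65% overall the smallest expected count will nearly always fall below 5. If the 81% came from a chi-square or another large-sample calculation, it describes a test the plan will seldom use.

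Two things are at stake. The power calculation is the only quantitative justification for the sample size. And Section 4.2 hopes the results will lead to a phase III trial, so a higher chance of missing a real effect matters. The silence on sidedness adds a second risk: a choice that can change the conclusion is left open until after the data are seen.

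**Working it through.** **Inputs (Sections 1.4 and 16).** n = 10 evaluable per group; placebo rate 0.90; active rate 0.40; alpha 0.05 one-sided in the power statement; chi-square unless the smallest expected count is below 5, then Fisher.

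**Step 1: reproduce the 81%.** Let X ~ Bin(10, 0.9) be the placebo events and Y ~ Bin(10, 0.4) the active events. For each x, let c(x) be the largest y at which the test rejects. Then power = Σ P(X = x) · P(Y ≤ c(x)).

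The one-sided uncorrected chi-square test rejects at the following cut-offs (smaller x adds nothing visible):

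| x | P(X = x) | c(x) | P(Y ≤ c) | product |
|---|---|---|---|---|
| 10 | 0.3487 | 7 | 0.9877 | 0.3444 |
| 9 | 0.3874 | 5 | 0.8338 | 0.3230 |
| 8 | 0.1937 | 4 | 0.6331 | 0.1226 |
| 7 | 0.0574 | 3 | 0.3823 | 0.0219 |
| 6 | 0.0112 | 2 | 0.1673 | 0.0019 |
| 5 | 0.0015 | 1 | 0.0464 | 0.0001 |

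The sum is **0.814**. The arcsine approximation gives Φ(h√5 − 1.645) with h = 2·arcsin√0.9 − 2·arcsin√0.4 = 1.1287, which is Φ(0.879) = **0.810**. Other one-sided normal approximations give 0.794 (pooled), 0.866 (unpooled) and 0.607 (continuity-corrected).

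**Step 2: which test the rule selects.** With equal groups the smallest expected count is min(m, 20 − m)/2, where m is the total number of events. It is at least 5 only if m = 10. Under the planning rates the expected m is 9 + 4 = 13 and P(m = 10) = 0.057, so Fisher is used with probability 0.943. In the planned result itself (9/10 v 4/10, m = 13) the smallest expected count is 7/2 = 3.5, so Fisher applies.

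**Step 3: power of the planned rule, one-sided 0.05.**

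| x | P(X = x) | c(x) | P(Y ≤ c) | product |
|---|---|---|---|---|
| 10 | 0.3487 | 6 | 0.9452 | 0.3296 |
| 9 | 0.3874 | 4 | 0.6331 | 0.2453 |
| 8 | 0.1937 | 3 | 0.3823 | 0.0741 |
| 7 | 0.0574 | 3 | 0.3823 | 0.0219 |
| 6 | 0.0112 | 1 | 0.0464 | 0.0005 |

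The sum is **0.671**. Fisher alone gives 0.659; the difference is the single table 7/10 v 3/10, where m = 10 and chi-square applies (probability 0.012). Most of the loss against Step 1 comes from 9/10 v 5/10 (probability 0.078), 8/10 v 4/10 (0.049) and 10/10 v 7/10 (0.015). Chi-square rejects at these three; Fisher does not.

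**Step 4: the same rule two-sided at 0.05.** The cut-offs become 5, 3, 2, 1 and 0 for x = 10, 9, 8, 7 and 6: 0.2907 + 0.1481 + 0.0324 + 0.0027 + 0.0001 = **0.474**.

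**Step 5: the planned result.** For 9/10 v 4/10, Fisher one-sided p = [C(10,9)·C(10,4) + C(10,10)·C(10,3)] / C(20,13) = (2100 + 120)/77520 = **0.029**. The two-sided p is **0.057**.

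**Step 6: type I error.** Over common event rates, the one-sided chi-square used throughout reaches 0.058. The planned rule stays at or below 0.035.

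**Step 7: what it would take.** One-sided, the planned rule reaches 80.9% if the active rate falls to 32% and 83.9% at 30% (Fisher alone: 82.4% at 30%). At 90% v 40% it first reaches 80% with 12 evaluable per group one-sided (81.1%), or 15 per group two-sided (82.3%).

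**The case against.** - **The 81% is not miscalculated.** It can be reproduced, and because the documents name no method its source can only be inferred. That stands. The fault is a mismatch between the power method and the analysis, whether chi-square or arcsine was used; neither reflects Fisher's test.
- **One-sided is the natural reading.** All three power statements say one-sided, and no two-sided primary test appears anywhere. That is fair: 67% is the main figure, and 47% is what follows only if the test is run two-sided. One sentence in Section 16 would settle it. It still matters, because at the planned result that choice decides significance.
- **More than 20 are randomized.** Section 2.1 says "Approximately 24 subjects will be randomized in a 1:1 ratio", and at 12 evaluable per group the rule would have 81.1% (75.0% at 11). But the plan attaches 81% to 10 evaluable per group and recruits an "additional 4 subjects to account for a 20% drop out/study non-compliance rate". Losing 20% of 24 leaves 19.2 patients, so 12 per group cannot be assumed.
- **It is a pilot, and the rule is conservative.** False positives are not inflated. The harm is a higher miss rate and an optimistic statement of power. Even so, Sections 1.4 and 2.3 present 20 evaluable patients as the number required for 81%.

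**Conclusion.** The concern holds. At 10 evaluable per group and 90% v 40%, the planned chi-square/Fisher rule has 67.1% power at one-sided 0.05, about 14 points below the 81% stated in three sections. The chance of missing the planned effect is 33% instead of 19%, and 53% if the test were run two-sided. These are exact figures that rest only on the plan's own rates, group size and switching rule. They would change with the number evaluable. Using chi-square throughout is not a way back to 81%, because its one-sided type I error then exceeds the stated 5%. Because a stated power is wrong for the planned test and the test's sidedness is undefined, both should be corrected before unblinding.

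**What to change.** 1. In Sections 1.4, 2.3 and 16, replace 81% with 67% for the planned test at one-sided 0.05, and name the method (exact enumeration of the chi-square/Fisher rule). Reword the sentences that present 20 evaluable patients as the number needed for 81%.
2. In Section 16, state that the primary comparison is tested one-sided at 0.05.
3. Optional: replace the data-dependent switch with one pre-specified one-sided Boschloo exact test. At 10 per group it has 78.7% power with type I error at most 0.045; then state 79%.

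The cost is wording in three sections and a less favourable stated power. No extra patients are needed, and Boschloo's test is in standard software. If the sponsor prefers to keep about 81% with the present rule, that takes 12 evaluable per group. With the plan's 20% loss this means 24/0.8 = 30 randomized instead of 24.

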## **17. ANALYSIS**

### **17.1 Safety Analysis**

Given the pilot nature of this study and limited number of participants, there will be no formal planned interim safety analysis unless an SAE is documented and thought more likely than not directly related to the IP. We will conduct a safety analysis if deemed necessary upon review of the SAE by the DSMB. Otherwise safety analysis will be performed upon the conclusion of the study.

### **17.2 Efficacy Analysis**

Efficacy analysis will be conducted at the completion of the study.

## **17.3 Interim Analysis**

None planned.

## **18. REGULATORY OBLIGATIONS**

### **18.1 Informed Consent**

Before a subject's participation in the clinical study, the PI or identified designee is responsible for obtaining written informed consent from the subject after adequate explanation of the aims, methods, anticipated benefits, and potential hazards of the study and before any protocol specified procedures, investigational product, intervention or device are administered or initiated.

### **18.2 Institutional Review Board**

A copy of the protocol, proposed ICF, and all other applicable subject information will be submitted to the IRB for written approval. A copy of the written approval of the protocol and ICF must be on file at the institution before recruitment of subjects into the study.

The investigator is responsible for obtaining IRB approval/renewal at least annually throughout the duration of the study. Copies of the investigator's reports and the IRB continuance of approval must be on file at the institution.

The investigator must submit study information to the IRB as required by all applicable guidelines and requirements. The investigator will obtain IRB approval for subsequent protocol amendments; except changes to eliminate an immediate hazard to study subjects, and changes to the informed consent document from the IRB prior to implementation.

The investigator will notify the IRB of deviations from the protocol or serious adverse events occurring at the site and other serious adverse event reports occurring at or received from participating centers as applicable for multi-center trials following the IRB policies and procedures.

